DSA	Corporate Confidential Information	ac & MP trough levels		sCD40		sCD154	
		mL	mL	Sample No.	mL	Sample No.	mL
		4#		1301	3	1401	4
		4#		1302	3	1402	4
				1303	3	1403	4
				1304	3	1404	4
				1305	3	1405	4
				1306	3	1406	4
				1307	3	1407	4
				1308	3	1408	4
				1309	3	1409	4
				1310	3	1410	4
				1311	3	1411	4
				1312	3	1412	4
				1313	3	1413	4
				1314	3	1414	4
				1315	3	1415	4
				1316	3	1416	4
				1317	3	1417	4
				1318	3	1418	4
				1319	3	1419	4
				1320	3	1420	4
				1321	3	1421	4
				1322	3	1422	4
					66		88

Corporate Confidential Information

Corporate Confidential Information

Blood Log (Part 2):

Visit	Study Day (Name or Time Post-Dose)	Serum pregnancy *	Local Labs ^	Central Lab	Viral / TB serology / surveillance
		mL	mL	mL	mL
1	Day -28 to 1 (Screening)	5#	19#	6#	5#
99	Day -1 to 1 (Baseline)	5#	19#	6#	20#
101	Day 1 (Predose 1)		19#	6#	
101	Day 1 (EOI 1)‡				
101	Day 1 (6 hrs)		19	6	
102	Day 2 (24 hrs)		19	6	
103	Day 3 (48 hrs)		19	6	
104	Day 4 (72 hrs)		19	6	
105	Day 7				
106	Day 10	5			
107	Day 15		19	6	10
108	Day 29		19	6	10
109	Day 43				
110	Day 57	5	19	6	10
111	Day 85		19	6	10
112	Day 113		19	6	10
113	Day 141	5	19	6	15
114	Day 169		19	6	10
115	Day 197		19	6	10
116	Day 225	5	19	6	10
117	Day 253		19	6	10
118	Day 281		19	6	10
119	Day 309	5	19	6	10
120	Day 337		19	6	10
199	Day 364 / Study Completion	5		2.5	15
Study total		40	380	122.5	175
Total Blood Volume†					

% Only collected in Part 3.

* Only collected in Part 3.

Only for females of child-bearing potential. Pregnancy tests should be carried out according to local practice. Local laboratory tests include: hematology, urinalysis, serum chemistries, and coagulation parameters.

Only need to be performed once in a 12-hour period if Screening, Baseline and Day 1 occur in close proximity.

Only need to be performed once in a 12-hour period if screening
† Total blood volume is obtained over approximately 12 months

† EOI = End of Infusion (IV) or End of Injection (SC). Blood samples obtained immediately after infusion for IV-administered CE7533 or immediately after injection for SC-administered CE7533.

Corporate
Confidential
Information

Corporate
Confidential
Information

sCD40 ⁺	
Sample No.	Mean
2301	3
2302	3
2303	3
2304	3
2305	3
2306	3
2307	3
2308	3
2309	3
2310	3
2311	3
2312	3
2313	3
2314	3
2315	3
2316	3
2317	3
2318	3
	5

Diagnostic Point-of-Care %			PGx	
DRID	Sample No.	mL	Sample No.	mL
			2701	5
1	2601	3		
1	2602	3		
1	2603	3		
1	2604	3		
1	2605	3		
1	2606	3		
1	2607	3		
2	2608	3		
3	2609	3	2702	5
4	2610	3		
5	2611	3		
6	2612	3		
7	2613	3		
8	2614	3		
9	2615	3		
10	2616	3		
11	2617	3	2703	5
12	2618	3		
13	2619	3		
14	2620	3		
		60		15
				1152

Corporate Confidential Information

14 Appendix 2: US-Specific CellCept(R) Pregnancy and Safety Information

- Use of CellCept® during pregnancy is associated with an increased risk of first trimester pregnancy loss and an increased risk of congenital malformations, especially external ear and other facial abnormalities including cleft lip and palate, and anomalies of the distal limbs, heart, esophagus, and kidney.
- Females of reproductive potential must be made aware of the increased risk of first trimester pregnancy loss and congenital malformations with MPA products and must be counseled regarding pregnancy prevention and planning.
- For those females using Cellcept® at any time during pregnancy and those becoming pregnant within 6 weeks of discontinuing therapy, the Investigator or healthcare practitioner should report the pregnancy to the Mycophenolate Pregnancy Registry ([name]). The Investigator or healthcare practitioner should strongly encourage the patient to enroll in the pregnancy registry.
- Risks and benefits of CellCept® should be discussed with the patient. When appropriate, consider alternative immunosuppressants with less potential for embryofetal toxicity. In certain situations, the patient and her healthcare practitioner may decide that the maternal benefits outweigh the risks to the fetus. If this drug is used during pregnancy, or if the patient becomes pregnant while taking this drug, the patient should be apprised of the potential hazard to the fetus.
- To prevent unplanned exposure during pregnancy, females of reproductive potential should have a serum or urine pregnancy test with a sensitivity of at least 25 mIU/mL immediately before starting CellCept®. Another pregnancy test with the same sensitivity should be done 8 to 10 days later. Repeat pregnancy tests should be performed during routine follow-up visits. Results of all pregnancy tests should be discussed with the patient.
- Females of reproductive potential taking CellCept® must receive contraceptive counseling and use acceptable contraception (see [Table 14-1](#) for Acceptable Contraception Methods). Patients must use acceptable birth control during entire CellCept® therapy, and for 6 weeks after stopping CellCept®, unless the patient chooses abstinence (she chooses to avoid heterosexual intercourse completely).
- Patients should be aware that CellCept® reduces blood levels of the hormones in the oral contraceptive pill and could theoretically reduce its effectiveness.

Table 14-1 Acceptable Contraception Methods for Females of Reproductive Potential*

Option 1 Methods to Use Alone	
 • Intrauterine device (IUD) • Tubal sterilization • Patient's partner had a vasectomy 		
OR			
Option 2 Choose One Hormonal Method AND One Barrier Method	Hormone Methods choose 1		Barrier Methods choose 1
	Estrogen and Progesterone 
 • Oral contraceptive pill • Transdermal patch • Vaginal ring Progesterone-only 
 • Injection • Implant 	AND	
 • Diaphragm with spermicide • Cervical cap with spermicide • Contraceptive sponge • Male condom • Female condom
OR			
Option 3 Choose One Barrier Method From Each Column (must choose two methods)	Barrier Methods choose 1		Barrier Methods choose 1
	
 • Diaphragm with spermicide • Cervical cap with spermicide • Contraceptive sponge 	AND	
 • Male condom • Female condom

*Females of reproductive potential include girls who have entered puberty and all women who have a uterus and have not passed through menopause.

15 Appendix 3: Stopping rules

Transition rules are based on both efficacy and safety results from Part 2. In Part 2, treatment arms are as follows:

- A: CFZ533 10mg/kg (IV);
- B is Control

Then the rules are as follows:

- If A is terminated for any reason, then STOP the study.

The following rules are for terminating treatment group(s) from Part 2:

For safety:

- Terminate the treatment group if there are two (2) or more patients presenting with PTLD or PML in that group.
- For toxicities, AEs / infections, and causalities, case-by-case review is needed to determine any treatment group(s) should be terminated.

For efficacy (based on the number of patients with tBPAR):

- If no tBPAR for SoC, then any group with tBPAR ≥ 7 will be terminated.
- If one tBPAR for SoC, then any group with tBPAR ≥ 8 will be terminated.
- If more than one tBPAR for SoC, then any group with tBPAR ≥ 9 will be terminated.

16 Appendix 4: Guidelines for MMF dose reduction

An Investigator may interrupt temporarily or reduce the dosage of study medication MMF if in his/her opinion this is clinically warranted, in response to any causally associated AE (e.g., neutropenia, thrombocytopenia, leucopenia, hyperlipidemia, hypertriglyceridemia or gastrointestinal intolerance). The following guidelines should be followed:

Dose reduction or temporary interruption may be performed for MMF

Implementation of dose reduction will be based on thrombocytopenia, leukopenia, neutropenia, or other AEs which are suspected to be related to study medication, and in the opinion of the Investigator, are clinically warranted. The following guidelines should be used for both dose reduction and, once the event has resolved, restarting or increasing the dose of MMF back to original levels.

Dose Reduction Guidelines

Platelets

- platelet count $< 100,000/\text{mm}^3$ dose **may** be reduced at the discretion of the Investigator
- platelet count $< 75,000/\text{mm}^3$ a second dose reduction should be **considered**
- platelet count $< 50,000/\text{mm}^3$ **MANDATORY** interruption of medication

WBC

- WBC $< 3500/\text{mm}^3$ dose **may** be reduced at the discretion of the Investigator
- WBC $< 2500/\text{mm}^3$ a second dose reduction should be **considered**
- WBC $< 2000/\text{mm}^3$ **MANDATORY** interruption of medication

All these changes must be recorded on the MMF Dosage Administration Record eCRF.

17 Appendix 5: Tacrolimus drug-drug interactions

Please refer to most recent national prescribing information for current labeling recommendations.

Drug interactions

Due to the potential for additive or synergistic impairment of renal function, care should be taken when administering Tac with drugs that may be associated with renal dysfunction. These include, but are not limited to, aminoglycosides, amphotericin B, and cisplatin. Initial clinical experience with the co-administration of Tac and cyclosporine resulted in additive/synergistic nephrotoxicity.

Drugs that may alter tacrolimus concentrations

Since Tac is metabolized mainly by the CYP3A enzyme systems, substances known to inhibit these enzymes may decrease the metabolism or increase bioavailability of Tac as indicated by increased whole blood or plasma concentrations. Drugs known to induce these enzyme systems may result in an increased metabolism of Tac or decreased bioavailability as indicated by decreased whole blood or plasma concentrations. Monitoring of blood concentrations and appropriate dosage adjustments are essential when such drugs are used concomitantly.

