3.1.4 Part 2 – Arms 2A-2B

Figure 3-3 Part 2 Design

Approximately 45 patients who meet the inclusion criteria will be randomized in a 2:1 fashion within 24 hours pre-transplant to receive one of the 2 treatment arms (Figure 3-3):

1. **Arm 2A**, n=30: Basiliximab 20 mg (Days 1, 4) + **CFZ533 at 10 mg/kg IV** (17 doses) + MMF 1.0g BID + CS
2. **Arm 2B Control/SoC**, n=15: Basiliximab 20 mg (Days 1, 4) + Tac (4-11 ng/mL) + MMF 1.0 g BID + CS

Induction therapy must be started within 2 hours prior to transplantation, or according to local practice.

The first dose of CFZ533 will be administered IV pre-transplant or intra-operatively. Drug administration will begin after randomization and must be completed by the time of unclamping. Subsequent doses of CFZ533 will be administered IV (Arm 2A), over a period of 12 months.

Other study drugs (apart from Basiliximab) should be started within 24 hours post-transplant. The second dose of basiliximab will be administered on Day 4, or according to local practice.

The day of randomization and transplant will be considered to be study Day 1. Further treatment will be given on study Days 3, 7, 15, 29, 43, 57 and then monthly thereafter until Months 12 (up to approximately Day 337). Subjects will then undergo Study Completion evaluations.

The primary endpoint of Part 2 will be assessed to determine whether the success criteria (safety and tBPAR) have been met

Corporate Confidential Information

Corporate Confidential Information

If notable AEs or safety concerns meeting the *a priori*-defined stopping criteria (see [Section 5.5.10](#)) one of the planned dose levels may be changed or discontinued via amendment.

Subjects will undergo Study Completion evaluations at the end of the trial.

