5.5.10 Discontinuation of study treatment and premature subject withdrawal

Study “Stopping rules”

The following stopping rules based on potential toxicities will serve as the basis for placing the study on hold. Although the stopping criteria do not incorporate an absolute requirement for causality, the potential relationship between an AE and CFZ533 will be evaluated carefully on a case-by-case basis between the Sponsor and the Investigator. Following a review of the AE(s), a decision to permanently discontinue enrollment or re-initiate dosing will be made by the DMC.

- Two (2) or more patients presenting with PTLD or PML

In addition, specific stopping rules for the incidence of tBPAR will be applied. These rules are designed to ensure that a CFZ533 treatment arm will be stopped if there is high probability (>90%) that the true tBPAR rate is greater than 20%. Corporate Confidential Information

Corporate Confidential Information

In addition to the automatic hold criteria and tBPAR criteria presented above, the DMC will review safety data regularly as outlined in their charter (see [Section 8.4](#)) during quarterly and *ad hoc* meetings. The DMC can recommend stopping a specific study arm(s) or the entire trial if significant changes or effects that, in their collective opinion, are deemed unsafe or unethical to continue administering CFZ533.

Discontinuation of study regimen

The Dosage Administration Records for CFZ533 (all parts), MMF and Tac (Part 1 only) and Concomitant Medication eCRF for MMF and Tac (Part 2) will be used to record if a subject has permanently discontinued study treatment and why.

Possible reasons for study treatment discontinuation are:

- Adverse Event
- Lack of Efficacy
- Technical problem during transplant surgery
- Subject/Guardian Decision
- Lost to follow-up
- Death
- Graft Loss

The Investigator should discontinue a subject from their randomized treatment regimen if, on balance, he/she believes that continuation would be detrimental to the subject's well-being.

Subjects who become pregnant while taking study medication must be discontinued from study medication and from the study, such pregnancies should be reported as SAEs to Novartis DSE and entered as AEs in the eCRF, the reason for discontinuation of study medication should be recorded as AE and reason for discontinuation from study is pregnancy (see next section below).

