5.5.13 Replacement of early withdrawals or discontinuations

The sponsor allows for over-recruitment of 2 patients in Part 1 and additional 10% in Part 2, to compensate for potential early withdrawals or discontinuations from the study.

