1.4.3 Study “stopping” rules

The following stopping rules based on potential toxicities will serve as the basis for placing the study on hold. Although the stopping criteria do not incorporate an absolute requirement for causality, the potential relationship between an AE and CFZ533 will be evaluated carefully on a case-by-case basis between the Sponsor and the Investigator. Following a review of the AE(s), a decision to permanently discontinue enrollment or re-initiate CFZ533 dosing will be made by the DMC.

- Two (2) or more patients presenting with post-transplant lymphoproliferative disease or progressive multifocal leukoencephalopathy in the CFZ533 treatment arm.

In addition, specific stopping rules for the incidence of tBPAR will be applied. These rules are designed to ensure that an arm will be stopped if there is high probability ($> 90\%$) that the true tBPAR rate is greater than 20%. Based on this stopping rule, the maximum number of patients with tBPAR for various different illustrative sample sizes would be as follows:

Table 1-1 Study stopping rules for tBPAR

Total number of patients (N)	Number of patients with tBPAR that would lead to stopping the treatment arm (n)	Observed tBPAR rate (n/N)
3	2	0.67
4	2	0.50
5	3	0.60
6	3	0.50
7	3	0.43
8	4	0.50
9	4	0.44
10	4	0.40
11	5	0.45
12	5	0.42
13	5	0.38
14	5	0.36
15	6	0.40
16	6	0.38
17	6	0.35
18	6	0.33
19	7	0.37
20	7	0.35
21	7	0.33
22	7	0.32
23	8	0.35
24	8	0.33
25	8	0.32
26	8	0.319
27	9	0.33
28	9	0.32
29	9	0.31
30	9	0.30

In addition to the automatic hold criteria and tBPAR criteria presented above, the DMC will review safety data regularly as outlined in their charter during quarterly and ad hoc meetings. The DMC can recommend stopping a specific study arm(s) or the entire trial if significant changes or effects that, in their collective opinion, are deemed unsafe or unethical to continue administering CFZ533.

2 First interpretable results (FIR)

First interpretable results (FIR) will be provided for this trial.
Corporate Confidential Information

Corporate Confidential Information

4 Statistical methods: Analysis sets

For patients for which the actual treatment received does not match the randomized treatment, the treatment actually received will be used for the analysis.

The Full Analysis Set will include all patients that received at least one dose of study drug and who were transplanted.

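### The chance of progressing stated in Section 9.6 (above 80%) is not met under the ongoing monitoring the protocol describes, and the Appendix 3 stopping counts lack a denominator, a time point and a link to Section 5.5.10

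*Protocol*

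**What the plan says.** **Stopping rule.** Protocol Section 5.5.10 says that "a CFZ533 treatment arm will be stopped if there is high probability (>90%) that the true tBPAR rate is greater than 20" percent. SAP Section 1.4.3, Table 1-1, turns this into a count for each N from 3 to 30, ending at 9 of 30. Protocol Section 3.1.2 applies the rule at any time, and Section 5.4 has core team members reviewing data continuously to evaluate it.

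**Success criterion.** Protocol Section 9.4.2 requires a posterior probability above 60% that the CFZ533 rate exceeds the control rate by less than 0.20. The priors are Beta(1/3, 1/3) for CFZ533 and Beta(1, 13) for control.

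**Probability of progressing.** Section 9.6 defines progressing as passing both rules. It gives more than 80% for true CFZ533 rates below 20% with control around 10%, and about 80% probability of not progressing when CFZ533 is more than 25 points above control. It does not say how many stopping looks were assumed.

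**Appendix 3.** This opens with "Transition rules are based on both efficacy and safety results from Part 2" and states "If A is terminated for any reason, then STOP the study". Its efficacy lines run from "If no tBPAR for SoC, then any group with tBPAR ≥ 7 will be terminated", through 8 with one SoC event, to "If more than one tBPAR for SoC, then any group with tBPAR ≥ 9 will be terminated". None of them gives a number of patients or an assessment time.

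**Size.** Section 3.1.4 says "Approximately 45 patients who meet the inclusion criteria will be randomized in a 2:1 fashion within 24 hours pre-transplant", with arms of 30 and 15. Section 5.5.13 adds that "The sponsor allows for over-recruitment of 2 patients in Part 1 and additional 10% in Part 2".

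**The concern.** Two things looked wrong.

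First, a stopping rule checked repeatedly removes more trials than one checked once at the end. If Section 9.6 counted the rule only once, the probability that justifies the sample size is too favourable for the monitoring described elsewhere in the protocol.

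Second, Appendix 3 attaches the most severe consequence, ending the study, to bare counts. A DMC with 7 CFZ533 events and no control events would find termination in Appendix 3 and no stop at N=30 in Table 1-1. The readable text does not say which applies, at what enrolment, or whether events after Month 3 count.

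**Working it through.** **Formulas.** With r events among N on CFZ533 and s among M on control:

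- Stopping: S(r, N) = 1 − F(0.20; 1/3 + r, 1/3 + N − r) > 0.90, where F is the Beta distribution function.
- Success: the integral over c of F(c + 0.20; 1/3 + r, 1/3 + N − r) times the Beta(1 + s, 13 + M − s) density at c, > 0.60.

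**Reproducing the plan.** The stopping formula returns all 28 rows of Table 1-1. At N=30, S is 0.674 for 7 events, 0.812 for 8 and 0.904 for 9, so the threshold is 9. At 30/15 the success criterion first fails at 7, 8, 9 and 10 CFZ533 events for 0, 1, 2 and 3 control events.

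For Section 9.6, the success criterion alone gives 0.794 progressing at 20% v 10%, and 0.809 not progressing at 35% v 10%. One stopping look at N=30 gives 0.779 and 0.844. The stated figures are therefore close to a calculation with no stopping look or one.

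**Part 1: repeated looks.** P(progress) is the sum over s of Bin(s; 15, 0.10) times the probability that CFZ533 finishes 30 patients below the success limit for that s, without having reached the Table 1-1 count at any look. The recursion is exact. It assumes that each patient's 3-month outcome is known at the look.

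| Looks at the stopping rule | 15% | 18% | 19% | 20% | 80% held up to a true rate of about |
|---|---|---|---|---|---|
| None (success only) | 0.936 | 0.861 | 0.829 | 0.794 | 19.8% |
| N=30 only | 0.932 | 0.852 | 0.817 | 0.779 | 19.4% |
| N=10, 20, 30 | 0.898 | 0.804 | 0.765 | 0.724 | 18.1% |
| Every 5 patients | 0.887 | 0.789 | 0.750 | 0.708 | 17.7% |
| Every patient from N=10 | 0.881 | 0.777 | 0.736 | 0.693 | 17.4% |
| Every patient from N=3 | 0.805 | 0.696 | 0.655 | 0.613 | 15.1% |

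With one look, the value at 19.5% is 0.799.

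**Part 2: Appendix 3 at the planned size.** Combining {success fails} with {9 or more events} at 30/15 gives limits of 7, 8, 9, 9 for 0, 1, 2, and 3 or more control events. These are the Appendix 3 counts: all 31 × 16 = 496 cells agree. Three cells trigger Appendix 3 but not Section 5.5.10:

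- 7/30 v 0/15, S = 0.674
- 8/30 v 0/15, S = 0.812
- 8/30 v 1/15, S = 0.812

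With control at 10%, their combined probability is 0.7%, 4.0%, 9.2% and 12.2% at true CFZ533 rates of 10%, 15%, 20% and 25%.

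**Part 2: with over-recruitment.** Ten percent more is 30 × 1.1 = 33 and 15 × 1.1 = 16.5. Extending the 90% rule past the end of Table 1-1 gives a threshold of 10 at N=31 to 33. At about 2:1 (31/15 to 33/17), the combined limits become 7, 8, 9, 10. The only departure is exactly 9 CFZ533 events with 3 or more control events, where Appendix 3 terminates although success is met and the 90% rule is not:

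- 9/31 v 3/15: success 0.666, S = 0.886
- 9/33 v 3/16: success 0.719, S = 0.843

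At 20% v 10%, the probability of this departure is 1.4% at 31/15, 2.0% at 33/16 and 2.2% at 33/17.

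**The case against.** **On Section 9.6.** The sentence is offered as an example read from Figure 9-2, which the copy reviewed does not show. With one look it holds to about 19.4%, and with control at 12%, arguably still around 10%, to about 20.0%. A reader might infer that the figure is simply wrong. That is not supported: the one-look shortfall is 80 − 77.9 = 2.1 points at 20%. The larger shortfalls depend on look schedules that the documents do not give. Assuming complete 3-month outcomes at each look probably overstates early stopping, and SAP Section 1.4.3 calls its sample sizes illustrative. What stands is that Sections 3.1.2 and 5.4 do describe ongoing application, and that every multi-look schedule tried loses 80% well below 20%.

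**On Appendix 3.** The exact match at 30/15 shows where the counts come from, so the denominator can be inferred. The two rules can run as stop-if-either, and a stricter comparative rule beside an absolute one is a legitimate choice. The 0.7% to 12.2% above measures that choice, not an error rate. Redacted text in Sections 3.1.4, 5.5.10 and 9.4 may hold timing or precedence wording. These points stand. They make this a request to reconcile and label, not a finding of contradiction.

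**Stronger readings to avoid.**

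- That the counts cease to match once enrolment passes 30. At about 2:1 the lines for 0 and 1 control events still agree. Off that ratio more can move: at 33/15 the limits become 8, 9, 10, 10. An analysed N above 30 is itself an assumption, because over-recruitment is meant to offset withdrawals.
- That Appendix 3 misses failures below 30. At 28/14, 6 v 0, 7 v 1 and 8 v 2 fail the success criterion without reaching its counts, but Section 9.6 already blocks progression there.
- That the SAP's Month 6 re-evaluation conflicts with Appendix 3. The SAP was written against protocol v02, and the documents do not settle whether that step is current.

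**Conclusion.** The Section 9.6 point holds in limited form. With one final look the stated probability is met except within about half a point of 20%. Under monitoring of the kind the protocol describes, the probability at a 20% true rate is 0.724 with three looks and 0.613 with a check after every patient: 7.6 and 18.7 points below 80%. This rests on 30/15, control at 10%, complete outcomes at each look, and illustrative schedules.

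The Appendix 3 point also holds in limited form. Its counts reproduce the combined criteria at 30/15, but the text does not say so. It ends the study in three patterns where the 90% rule is not met, and no readable passage says how the rules combine. Over-recruitment at about 2:1 adds one rare mismatch, at about 1–2% for 20% v 10%. Confidence is moderate because of the redactions. The point should be fixed but does not invalidate the design.

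**What to change.** 1. Rerun the Section 9.6 probabilities and Figures 9-1 and 9-2 under the monitoring schedule actually used, and state that schedule. This costs a short computation and a somewhat less favourable stated figure.
2. Reconcile Appendix 3 with Section 5.5.10, Table 1-1 and Section 9.6. State the numbers of patients and the time point to which the counts apply, what happens if the analysed numbers differ from 30 and 15, and how the rules combine. Which rule governs is for the sponsor and the DMC. This costs protocol and SAP wording only, with no new patients or data.
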